8.4.2.2 Secondary Efficacy Analyses

In addition to the primary efficacy endpoint, analyses related to the secondary efficacy objectives will also be included in the double-blind analysis. The secondary efficacy assessment of change from baseline in UPRC at Day 113 will be assessed using a longitudinal (repeated measure) mixed model including treatment arm, baseline value UPRC and randomization stratification factors (genotype and Age), time (study days in which UPRC is measured), and time by treatment interaction as fixed effects and subject as a random effect. Adjusted mean, SE, 95% CI for adjusted mean difference between treatment arms will be provided. A similar mixed model will also be used to assess the change from baseline in serum albumin at Day 113. The model will include treatment group, baseline value serum albumin value and randomization stratification factors (genotype and age), time (study days in which serum albumin is measured), and time by treatment interaction as fixed effects and subject as a random effect. Adjusted mean, SE, 95% CI for adjusted mean difference between treatment arms will also be provided.

The secondary efficacy endpoint of proportion of subjects achieving complete remission (UPCR ≤ 0.3 with eGFR: normal or $\geq 75\%$ baseline if below normal at baseline) at Day 113 will be assessed using a logistic regression model similar to the one used for the primary efficacy endpoint. The logistic regression model will include treatment arm, stratification variables (Genotype and Age) and baseline UPCR as continuous variable and point estimate of adjusted ORs, corresponding 95% CI will be provided.

A summary of the analysis methods to be used for the analysis of the primary, secondary and exploratory efficacy endpoints are presented in [Table 8.4.3-1](#) below. Further details on the primary and secondary analyses along with exploratory evaluations, any additional sensitivity analyses and data handling details regarding issues such as missing data are provided in the Statistical Analysis Plan.

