3.2 Secondary Objectives

- 1) Assess improvement in change from baseline in the level of proteinuria following treatment with abatacept compared to placebo.
 - Assess difference in mean change from baseline in Urine Protein/Creatinine Ratio (UPCR) at Day 113.
- 2) Assess improvement in serum albumin levels following treatment with abatacept compared to placebo.
 - Assess difference in mean change from baseline in serum albumin at Day 113.

- 3) Assess improvement in complete remission while maintaining renal function following treatment with abatacept compared to placebo.
 - Assess difference in percent of subjects achieving complete remission ($UPCR \leq 0.3$) with preservation of eGFR at Day 113.
- 4) Assess improvement in patient reported outcomes related to nephrotic syndrome.
 - Assess changes using the Patient Reported Outcomes Measurement Information System (PROMIS) at Day 113.
- 5) Assess the safety and immunogenicity of abatacept in subjects with TRNS.
 - Describe rates of AEs and SAEs and immunogenicity testing.
- 6) Assess the pharmacokinetics of abatacept in subjects with TRNS.
 - Describe the pharmacokinetics of abatacept.

[REDACTED]

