7.1 General Methods

All construction of CIs for differences in response rates between treatment groups will be based on minimum risk weights⁴ to account for randomization stratification factors, unless otherwise noted. All construction of CIs for response rates within treatment group will be based on normal approximation, unless otherwise noted.

All construction of CIs for continuous measures will be based on a mixed effects model which includes treatment group, baseline value of variable, randomization stratification factors, time, time by treatment interaction, and baseline value by time interaction as fixed effects and subject as a random effect. An unstructured covariance matrix will be used to model the correlation of the repeated measures within each subject. The SAS procedure PROC MIXED will be used with the restricted maximum likelihood (REML) method for estimation and the denominator degrees of freedom will be calculated according to the Kenward Roger method. In case of non-convergence of the preferred longitudinal model, memory space issues or other computational issues the following back-up models are defined:

- In the first backup model, the repeated statement will specify a spatial power covariance matrix and intercept and slope will be specified as random effects on a subject level.
- In the second backup model, the model will not include terms for the interaction between the baseline variable and time.

Unless otherwise specified, summary statistics will include the following:

- Summary statistics for continuous variables will include means, standard deviations, median, quartiles, minima and maxima.
- Summary statistics for qualitative or discrete variables will include the count and percentage.

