- The proportion of subjects achieving complete remission (defined in [Section 8.1.2](#): UPCR ≤ 0.3 with eGFR normal or $\geq 75\%$ baseline if below normal at baseline) at Day 113: the comparison in proportion of subjects achieving complete remission between the abatacept and placebo arms will be assessed using a logistic regression model. To account for randomization stratification, the logistic regression model will adjust for the randomization stratification variables of genotype and age in addition to adjusting for baseline UPCR and baseline eGFR. Point estimate of the adjusted Odds Ratios (OR) of the odds of achieving complete remission in the IV abatacept arm compared to the placebo arm, corresponding 95% CI, will be provided.
- Mean change from baseline in PROMIS measures at Day 113. Descriptive summary statistics for changes in patient reported outcomes of physical function, fatigue and pain improvement from baseline over time during double-blind period for the PROMIS static short forms will be provided by age group.

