7.5.5 Subgroup Analysis

All analyses described in this section will be performed on the ITT Analysis Population. Table 7.5.5-1 shows the subgroups of interest for analyses of the primary efficacy endpoint of renal response. If the value of the grouping variable cannot be determined for a subject, the subject will be excluded from the corresponding subgroup analysis. Only subgroups consisting of 10% or more of the total study population will be considered.

Table 7.5.5-1: Subgroup of Interest of the Primary Efficacy Assessment of Renal Response

Subgroup Factor	Categories
APOL1	High Risk
	Other
Age	Pediatric (< 18 years)
	Adult (≥ 18 years)
Gender	Male
	Female
Race	Caucasian
	Black
	Asian
	Others
Baseline UPCR	Baseline UPCR < 6mg/mg
	6mg/mg ≤ Baseline UPCR < 9mg/mg
	Baseline UPCR ≥ 9mg/mg
Diagnosis	FSGS
	MCD

The proportion of subjects who achieve renal response, defined by composite renal index, at Day 113 at the end of double-blind period in abatacept and placebo arm will be summarized using point estimates and 95% confidence interval for each treatment group by subgroup. The difference in proportions between treatment groups for each subgroup will be provided by point estimate and 2-

sided 95% confidence interval using normal approximation, without any adjustments for strata, if the number of events in each individual treatment group is at least 5. Otherwise, confidence intervals using an exact method will be provided.

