8.1.2 Complete remission

Complete remission at a specific time point will be present if all the following criteria are met at that time point:

PROTEINURIA: UPCR \leq 0.3.

RENAL FUNCTION: No worsening of baseline (Study Day 1) estimated glomerular filtration rate (eGFR) defined as within normal range if normal at baseline, or \geq 75% baseline value if below normal at baseline.

eGFR determination will be based on the CKD-EPI for adults and the new Schwartz equation for children as indicated in [Section 8.1.1](#) above.

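### Complete remission is planned as an odds ratio with no provision for an empty arm, and the difference in percent named in the objective is not called for

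*SAP*

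**What the plan says.** - **Objective.** Secondary objective 3 (SAP 3.2, and the same in the protocol) is to "Assess difference in percent of subjects achieving complete remission" with preserved eGFR at Day 113.
- **Analysis.** SAP 7.5.3 fits a logistic regression with treatment, genotype, age, baseline UPCR and baseline eGFR, and reports "Point estimate of the adjusted Odds Ratios (OR) of the odds of achieving complete remission in the IV abatacept arm" relative to placebo with a 95% CI. Protocol 8.4.2.2 agrees on the output: "point estimate of adjusted ORs, corresponding 95% CI will be provided". Neither lists a p-value or a risk difference for this endpoint. Protocol Table 8.4.3-1 labels the row as differences in proportions, but the method beside it is the odds ratio.
- **Definition.** SAP 8.1.2: "Complete remission at a specific time point will be present if all the following criteria are met at that time point". The criteria are UPCR of 0.3 or less and the same eGFR rule as renal response. Under SAP 8.2, subjects who discontinue early or lack a response component count as non-responders.
- **General conventions.** SAP 7.1: "All construction of CIs for differences in response rates between treatment groups will be based on minimum risk weights", unless otherwise noted. It attaches no condition on event counts. Its back-up models cover only the longitudinal mixed model. It also says: "Summary statistics for qualitative or discrete variables will include the count and percentage".
- **Sparse counts elsewhere.** SAP 7.5.5 uses the normal approximation for renal-response subgroup differences "if the number of events in each individual treatment group is at least 5. Otherwise, confidence intervals using an exact method will be provided". That rule is confined to those subgroups.

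**The concern.** Complete remission is the rarer of the two binary endpoints, and it is analysed with a five-term logistic model in about 90 subjects. If remissions occur on abatacept and none on placebo, the likelihood keeps rising as the treatment coefficient grows, so the planned odds ratio and its CI have no finite value. That is the most favourable pattern the drug could show, and it is where the one planned between-arm result fails. With no p-value planned, the estimate and its interval are the whole result for this endpoint. A replacement method chosen after unblinding would be a choice made with the data in view.

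The second part is a mismatch of scale. The objective is worded as a difference in percent, and the endpoint's own section does not ask for one.

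**Working it through.** **Inputs.** SAP section 5 gives 90 subjects randomised 1:1, so 45 per arm, with assumed renal-response rates of 40% and 12%, two-sided alpha of 5% and about 80% power. No complete-remission rate appears in either document, so the rates below are assumptions.

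**The plan's own figure.** The uncorrected two-proportion formula at 80% power gives

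n0 = [1.96 × √(2 × 0.26 × 0.74) + 0.8416 × √(0.40 × 0.60 + 0.12 × 0.88)]² / 0.28² = 37.3, or 38 per arm.

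The continuity correction gives

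n = (n0/4) × [1 + √(1 + 4/(n0 × 0.28))]² = 44.2, or 45 per arm.

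This matches the plan's 90 subjects.

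**Choosing the range of rates.** A UPCR of 0.3 or less is also a fall of at least 50% whenever baseline UPCR is 0.6 or more. Entry requires at least 3 at screening, and the eGFR rule is shared. Complete remission is therefore nested in renal response, and the placebo remission rate cannot exceed the true placebo response rate. The 12% in the plan is a planning value for that response rate, based on one earlier study and expert opinion. It is a sensible top of the range but not a proven ceiling.

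**Chance of an empty placebo arm**, (1 − p)^45, and **chance that at least one arm is empty**, 1 − [1 − (1 − p)^45] × [1 − (1 − q)^45], for assumed placebo rate p and abatacept rate q:

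| Placebo p | Placebo arm empty | Either arm empty, q = 10% | Either arm empty, q = 20% |
|---|---|---|---|
| 1% | 63.6% | 63.9% | 63.6% |
| 2% | 40.3% | 40.8% | 40.3% |
| 3% | 25.4% | 26.0% | 25.4% |
| 5% | 9.9% | 10.7% | 9.9% |
| 8% | 2.3% | 3.2% | 2.3% |
| 12% | 0.3% | 1.2% | 0.3% |

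In a simulation of the five-term model (2,000 trials per rate; 25% high-risk genotype and 40% paediatric assumed; covariates unrelated to outcome), the covariates added less than 0.5 point to the chance of a non-finite treatment odds ratio. The empty arm is what drives the failure.

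**What failure looks like.** With assumed counts of 4/45 against 0/45, an ordinary unadjusted fit gave log odds ratios of 7.2, 14.2 and 24.2 after 8, 15 and 25 iterations, with standard errors of 10.8, 358 and 53,088. Any number printed depends on where the software stops.

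**What the alternatives give.** With assumed counts of 5/45 against 0/45:
- The ordinary odds ratio is infinite.
- Firth, which in this unadjusted two-by-two case adds 0.5 to each cell, gives (5.5/40.5)/(0.5/45.5) = 12.4, with a profile-likelihood CI of 1.3 to 1,641.
- The risk difference is 5/45 = 11.1 points, with an exact unconditional CI of about 2.2 to 24.0 points.
- Fisher's p is 0.056.

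**Coverage**, with abatacept at an assumed 10% and placebo across the six rates:
- The Firth profile interval covers 95.8 to 97.8% (1,000 simulated trials per rate, Monte Carlo standard error about 0.6 point).
- The exact unconditional difference interval, from two one-sided 2.5% score tests, covers 95.3 to 97.6% by full enumeration.

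**The case against.** The strongest reply is that SAP 7.1 already sets a CI method for differences in response rates. A difference stays computable when an arm is empty, so a reader who infers that objective 3 could be left with no between-arm result at all goes too far. This stands. What remains is that 7.5.3 does not call for the difference and 7.1 has no low-count rule. The minimum-risk-weight interval was not evaluated here, so nothing above shows that it performs badly.

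Three further inferences are tempting, and the documents do not support them.
- **Treating 12% as a ceiling.** The chance of fewer than 5 placebo remissions is 35.9% at a rate of 12%, and a reader might call that a minimum. At an assumed 15% it is 17.5%. Because 12% is only a planning value, no minimum follows.
- **Using the 5-event rule as the mark of failure.** SAP 7.5.5 uses it to choose between CI methods for unadjusted subgroup differences. An odds ratio does not fail below 5 events; it fails when an arm is empty. The rule shows only that sparse counts were foreseen elsewhere.
- **Asserting that no rule exists anywhere.** The available SAP text passes from 7.5.3 to 7.5.5, and SAP 7.5 refers to a section 7.5.4. A provision there cannot be excluded, although 7.5.3 reads as a complete account of this endpoint. Likewise, an ordinary fit is inferred, because the SAP says only logistic regression.

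It is also fair to say that a conditional fallback would suffice when events are plentiful. Using the same method whatever the count is preferable only because no choice then depends on the data.

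**Conclusion.** The point holds in limited form. The visible plan reports complete remission between arms as an adjusted odds ratio, makes no provision for an empty arm, and does not call for the difference in percent that the objective names. The chance that the placebo arm is empty runs from 64% at an assumed rate of 1% to 0.3% at 12%. It is 10% or more only if the true placebo rate is about 5% or lower. These figures assume 45 analysed per arm and rates that the documents do not supply. Non-responder imputation pushes counts down, by an amount that cannot be stated because no dropout rate is given.

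The consequence is modest: an unusable odds ratio and interval for one secondary endpoint of a pilot, with no p-value planned and counts and percentages still reported. It does not touch the primary analysis or the type I error. It deserves correction because the failure falls on the most favourable result and the repair is cheap.

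**What to change.** Amend SAP 7.5.3 for complete remission before database lock and unblinding. SAP 2.3 keeps sponsor personnel blinded until then.

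1. Estimate the odds ratio by Firth-penalised logistic regression with the same covariates (treatment, genotype, age, baseline UPCR, baseline eGFR) and give a profile-likelihood 95% CI.
2. Report the count and percentage in each arm and the risk difference named in objective 3, with one pre-chosen CI valid at low counts (exact unconditional or score-based). State that for this endpoint it replaces the minimum-risk-weight interval of SAP 7.1.

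Apply both whatever the number of events.

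The cost is a few sentences and standard software options. Firth estimation shrinks the odds ratio slightly, and its upper limit is very wide when an arm is empty. The difference interval is unstratified, and the exact version is somewhat conservative. In the 5/45 against 0/45 example both intervals exclude the null while Fisher's p is 0.056, so the SAP should also say that the complete-remission result is read as descriptive. The Firth coverage figures rest on covariates unrelated to outcome.

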Eligibility will be based on specified inclusion and exclusion criteria, medical history, disease activity and safety assessments. Randomization should occur within 28 days of signing the informed consent. This may be extended to 42 days to allow for screening results (eg, TB, *APOL1* SNP, UPCR and eGFR).

3.1.2 Double-Blind Period (Day 1 - Day 113):

On Day 1, subjects will be randomized to one of two blinded parallel treatment arms in a 1:1 ratio:

Abatacept IV

adults use weight-tiered dose:

< 60 kg:	500 mg
60 to 100 kg:	750 mg
> 100 kg:	1000 mg

pediatric patients 6 to 17 years:

< 75 kg:	10 mg/kg
≥ 75 kg	follow adult dosing.

Placebo (Normal Saline or D5W following the same dosing schedule).

Dosing is on Day 1, 15, 29, and then every 28 days.

The duration of the Double-Blind Period is 113 days.

There is an option to Early Escape into the OLE on Day 85 for pediatric age subjects only (< 18 years of age at randomization). The decision to Early Escape will be based on the Day 57 UPCR (> 3) and the assessment of clinical status on Day 85. If at the discretion of the investigator, in consultation with the subject (and their guardians), it is decided that the subject's clinical status has worsened or not improved sufficiently based on both of these criteria, the Day 85 visit may be skipped. The subject would complete the Double-Blind Period Early Termination visit ([Table 5.1-2](#)). The decision will then be made to either proceed to the OLE Day 1 visit ([Table 5.1-3](#)) or the Follow-up Visits ([Table 5.1-4](#)).

3.1.3 Open Label Extension (Day 1 - Day 169):

At the end of the Double Blind, there will be a 169 day open label extension (OLE). Subjects may enter this extension in 2 different manners. Subjects who reach the end of Double Blind will be able to volunteer to enter the OLE at the discretion of the investigators. Pediatric age subjects (6 to 17 years) who choose to Early Escape may then choose to enter the OLE. This includes both responder and non-responders who wish to determine if a longer exposure to abatacept could lead to a response. Abatacept will be administered every 28 days starting on Day 1 of the OLE (Day 1 of the OLE will be Day 113 of the Double Blind Treatment Period), without a loading dose. Adjustment in background therapy is allowed but limited. This includes increases or decreases in doses, including discontinuation, or change from one permitted agent to another (3.4.1.2, Restricted Treatments During Double-Blind).

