8.4.7 Outcomes Research Analyses

Descriptive summary statistics for changes in patient reported outcomes of physical function, fatigue and pain interference from baseline over time during the Double-Blind Period for the

PROMIS static short forms will be provided by age group (for subjects 18 and older: SF Physical Function v1.2 8b, SF Fatigue v1.0 Adult 8a and SF Pain Interference v1.0 Adult 8a; for subjects 17 and younger and their parent proxy: SF Physical Function - Mobility v1.0 Peds 8a, SF Fatigue v1.0 Peds 10a and SF Pain Interference v1.0 Peds 8a). Results for adults and pediatric subjects will be reported separately. The results for subjects 17 and younger will also be reported separately from their parent proxy form results. The mean change from baseline in these measures will be presented based on an analysis of covariance (ANCOVA) model.

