8.4 Missing Measurements

For determination of renal response, handling of missing values is addressed in [Section 8.2](#). For the analysis of individual components of other outcome research endpoints (Adult: SF Physical Function v1.2 8b, SF Fatigue v1.0 Adult 8a and SF Pain Interference v1.0 Adult 8a, Pediatric: SF Physical Function - Mobility v1.0 Peds 8a, SF Fatigue v1.0 Peds 10a and SF Pain Interference v1.0 Peds 8a), other efficacy measures and biomarkers, missing values will not be imputed. See the Safety Analysis Guidelines and Safety Data Conventions for the CTLA4IG program (Referenced earlier) for conventions related to the handling of missing or partial dates and the determination of appropriate default values in such cases and in particular for concomitant medication dose start-dates and end-dates and AE onset dates. All of these rules also apply when deriving efficacy data sets.

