8.6 Day Ranges for Analysis Time Points

Subjects do not always adhere strictly to the visit schedule timing in the protocol. Therefore the designation of visits during treatment will be based on the day of evaluation relative to the study (day of first infusion = study Day 1) rather than the nominal visit recorded in the case report form (CRF). Mutually exclusive relative day windows are defined in the following table to provide derived visits that correspond to the post-baseline time points specified in the protocol.

Designation of visits for efficacy assessments and outcomes research performed at every scheduled visit is tabulated in [Table 8.6-1](#).

Table 8.6-1: Day Ranges for Components of Renal Response, Component of Completed Remission and Outcomes Research Assessments at Every Scheduled Visit During the Double-Blind Period and OLE Period

Visit	Target Day	Component of Renal Response/ Complete Remission (UPCR, eGFR)	eGFR (Provided by Lab)	Outcomes Research Day Ranges
Double-blind period				
Screening	< 1	< 1	< 1	< 1
Day 1 (Baseline)	1	1	1	1
Day 15	15	8 - 22		
Day 29	29	23 - 43		
Day 57	57	44 - 71		
Day 85	85	72 - 99		2 - 99
Day 113*	113	100 - 127	50 - 177	100 - 127
OLE period				
Day 141	141	128 - 155		
Day 169	169	156 - 183		
Day 197	197	184 - 211		
Day 225	225	212 - 239		
Day 253	253	240 - 267		
Day 281	281	268 - 295		

* Day 113 assessment for subjects continuing in OLE, the upper inclusive limit of this window is the first infusion in OLE or 42 days after last dose in double-blind period, whichever comes earlier. Assessments within 42 days after last dose in double-blind period are included for subjects discontinuing during double-blind period.

For subjects who completed Period 1 and entered Period 2 prior to the protocol revision:

Table 8.6-2: For Subjects who Completed Period 1 and Entered Period 2 prior to the Protocol Revision

Visit	Target Day	Component of Renal Response/ Complete Remission (UPCR, eGFR)	eGFR (Provided by Lab)	Outcomes Research Day Ranges
Double-blind (Period 1 and Period 2)				
Screening	< 1	< 1	< 1	< 1

Table 8.6-2: For Subjects who Completed Period 1 and Entered Period 2 prior to the Protocol Revision

Visit	Target Day	Component of Renal Response/ Complete Remission (UPCR, eGFR)	eGFR (Provided by Lab)	Outcomes Research Day Ranges
Day 1 (Baseline)	1	1	1	1
Day 15	15	8 - 22		
Day 29	29	23 - 43		
Day 57	57	44 - 71		
Day 85	85	72 - 99		2 - 99
Day 113*	113	100 - 120	50 - 141	100 - 127
Day 128	128	121 - 134		

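### The pediatric Day 113 PROMIS result uses observed values only, so children who take early escape at about Day 85 drop out of it for reasons tied to their disease course

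*SAP*

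**What the plan says.** **Analysis.** Mean change in PROMIS at Day 113 is one of four secondary efficacy endpoints (SAP 4.2). SAP 7.5.3 plans: "Mean change from baseline in PROMIS measures at Day 113. Descriptive summary statistics for changes in patient reported outcomes", by age group and over time in the double-blind period. For the PROMIS forms, which SAP 8.4 names, and for "other efficacy measures and biomarkers, missing values will not be imputed". Protocol 8.4.7 goes further than the SAP: "The mean change from baseline in these measures will be presented based on an analysis of covariance (ANCOVA) model". It also states: "Results for adults and pediatric subjects will be reported separately".

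**Escape.** Protocol 3.1.2: "There is an option to Early Escape into the OLE on Day 85 for pediatric age subjects only". "The decision to Early Escape will be based on the Day 57 UPCR (> 3) and the assessment of clinical status on Day 85". It is at the investigator's discretion, in consultation with the subject and guardians, when "clinical status has worsened or not improved sufficiently based on both of these criteria".

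**Collection and windows.** Protocol Table 5.1-2 schedules PROMIS at Day 1, Day 85 and Day 113 or Early Termination. For a child who escapes, footnote a makes Day 85 the Early Termination visit. Tables 5.1-3 (OLE) and 5.1-4 (follow-up) list no PROMIS. SAP 8.6 assigns visits by study day, not by nominal visit, in windows that do not overlap. For outcomes research these are days 2-99 for Day 85 and days 100-127 for Day 113. For subjects continuing into the OLE, "the upper inclusive limit of this window is the first infusion in OLE" or 42 days after the last double-blind dose, whichever is earlier.

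**The concern.** Secondary objective 4 asks about PROMIS change at Day 113. For children, the Day 113 figure will come from those still in the double-blind period, and leaving it depends on how the disease has gone since randomization. If abatacept works, one would expect more children on placebo to qualify for escape and to take it. The loss would then differ by arm.

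The other three secondary efficacy endpoints have a way of keeping these children. Complete remission counts subjects who discontinue early as non-responders (SAP 8.2). UPCR and albumin use a repeated-measures mixed model that retains earlier visits (SAP 7.5.3). The PROMIS paragraph has neither. Amendment 02 introduced escape and SAP version 2.0 incorporates that amendment, yet the readable SAP mentions escape only in its amendment table.

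At stake is whether the pediatric Day 113 means, and any contrast between them, describe the randomized children or a subset selected after randomization.

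**Working it through.** **Step 1: where an escapee's PROMIS value goes**

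- Escape visit: Day 85. Applying the ±7-day dosing window of Protocol 4.5.2 to this visit gives 85 - 7 = 78 to 85 + 7 = 92.
- Outcomes-research window containing days 78-92: the Day 85 row (2-99).
- Lower bound of the Day 113 row: Day 100.
- Upper bound for an escapee who enters the OLE: the earlier of the first OLE infusion and the last double-blind dose plus 42 days. Table 5.1-3 puts OLE Day 1 on the day of the last double-blind visit, so days 78-92. With the last blinded dose at Day 57, 57 + 42 = 99; with a late dose at Day 64, 64 + 42 = 106. The earlier bound is always below 100.
- For an escapee who goes to follow-up instead, no further PROMIS is scheduled.

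On either route the Day 113 cell is empty. Nothing is imputed, so the child is absent from the Day 113 summary. An ANCOVA on observed Day 113 values would omit the same child.

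**Step 2: size, as an illustration only**

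The plan states no SD, effect size or power for PROMIS, so there is no PROMIS figure to reproduce. The only response rates given are 40% and 12% (Protocol 8.1, SAP 5). They do yield the stated power of about 80%. With 45 per arm and a continuity correction:

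z = (0.28 - 1/45 - 1.96 × √(2 × 0.26 × 0.74/45)) / √((0.40 × 0.60 + 0.12 × 0.88)/45) = 0.0765/0.0876 = 0.873, which is 80.9% power.

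Assumptions for the illustration:

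- Pediatric response rates equal the overall design rates.
- The PROMIS effect runs wholly through response, with D the responder minus non-responder difference and non-responders' mean change set to zero.
- The same fraction f of non-responders escapes in each arm, and no responder does.

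True contrast: (0.40 - 0.12) × D = 0.28D.

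Observed-case contrast: [0.40/(1 - 0.60f) - 0.12/(1 - 0.88f)] × D.

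| f | Missing, abatacept (0.60f) | Missing, placebo (0.88f) | Abatacept mean | Placebo mean | Contrast | Against 0.28D |
|---|---|---|---|---|---|---|
| 10% | 6% | 8.8% | 0.426D | 0.132D | 0.294D | +5% |
| 25% | 15% | 22% | 0.471D | 0.154D | 0.317D | +13% |
| 50% | 30% | 44% | 0.571D | 0.214D | 0.357D | +28% |
| 75% | 45% | 66% | 0.727D | 0.353D | 0.374D | +34% |
| 90% | 54% | 79.2% | 0.870D | 0.577D | 0.293D | +5% |
| 100% | 60% | 88% | 1.000D | 1.000D | 0 | -100% |

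Both arm means are overstated at every f. The contrast is inflated up to about f = 90% and understated beyond that. At an assumed D of 5 points, the true contrast is 1.40; it becomes 1.58 at f = 25% and 1.79 at f = 50%.

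**The case against.** The strongest counter-argument is the second sentence of the Table 8.6-1 footnote, which includes assessments within 42 days of the last blinded dose for subjects who discontinue in the double-blind period. A Day 85 visit is within 42 days of a Day 57 dose. One could therefore read the footnote as moving the Early Termination value into Day 113, in line with the protocol's combined column. That reading conflicts with non-overlapping windows assigned by study day. The sentence sets an upper limit and does not lower the Day 100 bound; the parallel footnote to Table 8.6-2 likewise speaks of extending the Day 113 assessment. If relabelling was intended, the SAP needs to say so.

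Second, SAP 7.1 makes the mixed model the default for confidence intervals on continuous measures, so it would govern any PROMIS interval. But the PROMIS paragraph promises descriptive statistics and no interval. SAP 7.5 also points to a section 7.5.4 that cannot be read in the public text, so further detail there cannot be excluded.

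Third, the numerical effect may be small. At D = 5 and f = 25% the shift is 0.18 points. With an assumed SD of 8 and 15 to 22 children per arm, the standard error of the contrast is 8 × √(2/15) = 2.9 to 8 × √(2/22) = 2.4. That stands. It limits the importance of the point but does not fill the empty cell.

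A reader might infer that the arms as a whole are compared only on subjects doing well enough to stay. The documents do not support that:

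- Adults cannot escape and are reported separately.
- Escape is optional, so some children who are not improving will stay and be counted.
- Escapees still contribute to the Day 85 summary.
- The criteria are UPCR and clinical status, not PROMIS, so the link to PROMIS is plausible but assumed.
- The SAP plans no formal PROMIS test between arms, and objective 4, unlike objectives 1 to 3, does not mention placebo.

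**Conclusion.** The point holds for the pediatric Day 113 PROMIS results. By the plan's own schedule and windows, children who escape have no Day 113 value, and they are selected on disease course. This is true of the SAP's descriptive summary and of the protocol's ANCOVA, and the two documents also differ on which of these is planned.

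The size and direction of bias cannot be derived from the documents. The figures of about +13% at 25% escape and +28% at 50% depend on the assumptions listed above, and the sign changes at very high escape rates. It would go too far to say that the bias must favor abatacept.

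The primary endpoint is unaffected, because subjects who discontinue early count as non-responders. This is a cheap improvement to one secondary endpoint and does not threaten the trial's main conclusion.

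**What to change.** In SAP 7.5.3:

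1. Estimate Day 113 PROMIS change with the SAP 7.1 repeated-measures mixed model, using the Day 85 and Day 113 visits so that an escapee's Early Termination value stays in through the Day 85 row. Fit it separately for each domain (physical function, fatigue, pain interference) in adults, child self-report and parent proxy. Drop the age stratum, which is constant within each fit.
2. Keep the observed-case table as a supplement, with the number of subjects contributing at each visit by arm.
3. Add a pediatric summary that takes the value from the protocol's Day 113 or Early Termination column as the end-of-period value, and state in SAP 8.6 how Early Termination PROMIS values are assigned.
4. Reconcile SAP 7.5.3 with the ANCOVA in Protocol 8.4.7.

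No new data are needed and the escape rule is untouched. The cost is SAP wording and up to nine fits (three domains by three respondent groups). The model assumes missing at random given the Day 85 value and the covariates. That is not guaranteed, because escape also depends on UPCR and clinical judgement, which are outside the PROMIS model. Pediatric numbers may be small, so estimates could be imprecise and the SAP 7.1 back-up models may be needed.
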